## 5. ASSESSMENTS

### 5.1 BASELINE ASSESSMENT

The baseline assessment will be conducted immediately following the screening and informed consent. The assessment will be interviewer-administered with the exception of sections deemed to ask sensitive questions, which will be self-administered by the participant.

Participants will be assessed as part of this study using validated interview instruments covering the following topics:

- Demographics, modified from the ASI Lite-CF Clinical/Training Version and Addiction Severity Index
- Opportunistic Infections, using questions adapted from the HIV Cost and Services Utilization Study (HCSUS)
- HIV Testing and HCV Diagnosis, using the HIV/HCV/STI Testing Status and Organizational Testing Practices Questionnaire
- Healthcare Utilization, using questions created by the Russian and US teams
- Barriers to Medical Care 
- Perceived Discrimination in Health Care
- ART Use and Adherence
- Medications
- Pain Assessments
- Reproductive Health
- HIV Sex Risk Behaviors, questions are adapted from the Women's Health Coop Baseline Questionnaire
- Sexual Partners, created by the US and Russian teams
- HIV Risk Categories, using questions adapted from the American Red Cross and Navaline et al.
- HIV Disclosure, using questions from Stein et al. (1998) and Raj et al. (2006)
- HIV Stigma, using the Berger et al. HIV stigma scale
- Substance Use Stigma
- Depressive symptoms through the Center for Epidemiologic Studies Depression Scale (CES-D)
- Anxiety by the State Trait Anxiety Inventory (STAI- Short Form)
- Partner Violence and Sexual Assault, adapted from the TAJ assessment
- Tobacco Use, using a shortened modified Fagerstrom Test for Nicotine Dependence
- Alcohol Use, via the AUDIT
- Opioid use disorder diagnosis via the DSM 5 criteria
- Drug use by an adapted version of the Risk Behavior Survey
- 30-Day Timeline Followback for Opioid Use
- Overdose and Suicide, using adapted questions from Britton et al. (2012)
- Social Support, using the harmonized STTR document
- VR-12 Health Survey & MOS-HIV
- Primary Activity
- Costs of Illness and Treatment in Last Month
- Attitudes Toward Care Coordination, using questions from Schang et al. (2013)
- Care Continuity, modified from Nijmegen Continuity Questionnaire

## 5.2 FOLLOW UP ASSESSMENTS

Content of assessments administered at the 6-, and 12- month visits will be subsets of the baseline assessment (see table below). Phone assessments will be permitted for 6 and 12 month (24 and 52

weeks) assessments, as a last resort, for participants who are unable to come in-person. Questions about COVID-19 will only be asked at one time-point, either the 6- or 12-month assessment.

Administered Assessment	Study Time Point			
	Baseline	Medication Check-Ins	6-Month	12-Month
Demographics	X			X
HIV Testing and HCV Diagnosis	X			X
ART Use and Adherence	X		X	X
Health Care Utilization	X		X	X
Costs of Illness and Treatment in Last Month	X		X	X
Attitudes Toward Care Coordination & Care Continuity	X		X	X
Barriers to Medical Care	X		X	X
Perceived Discrimination in Health Care	X		X	X
DSM-5 Opioid Use Disorder	X			
Drug Use	X		X	X
TLFB: Opioids	X	X	X	X
Tobacco Use	X			
Alcohol Use: AUDIT	X			X
Opportunistic Infections			X	X
Medications	X		X	X
Pain assessment			X	X
HIV Sex Risk Behaviors and Reproductive Health				X
*Sexual Partners	X			X
*HIV Risk Categories	X			
*HIV Disclosure	X		X	
*HIV Stigma	X			X
*Substance Use Stigma	X			X
*Barriers to Medical Care Part 2	X		X	X
*Depressive Symptoms (CES-D)	X			X
*Anxiety (GAD-7)	X			X
*Case Manager Questions			X	X
*Partner Violence and Sexual Assault			X	
Overdose and Suicide			X	X
Social Support Scale	X			
VR-12 Health Survey – MOS-HIV	X			X
Primary Activity	X		X	X
Visit Costs			X	X
COVID-19 Questions			X	X

#### 5.2.A. MEDICATION VISITS ASSESSMENTS

Medication symptoms and opioid use will be assessed during the medication check-in visits.

#### 5.3 SYSTEM-LEVEL ASSESSMENT OF LINC-II IMPACT

The system-level assessment will focus on provider, administrator, and patient perspectives and experiences with care coordination between the narcology and HIV care systems. System-level variables will be assessed from providers, administrators, and study participants (i.e., patients in the narcology or HIV care systems). Questions will assess demographics, role in the care system, attitudes toward care coordination, level of engagement in coordinated care, stigma toward patients with HIV and substance use disorders, and connection, if any, to LINC-II.

For the purpose of this study, care coordination will be defined as “the deliberate organization of patient care activities between two or more treatment settings involved in a patient’s care to facilitate the appropriate delivery of health care services,” referring in this case to the narcology and HIV care systems.

Providers and administrators will also be asked to what extent they are aware of LINC-II, if they have worked with a LINC-II CM, and what their experiences have been with LINC-II, including whether the presence of LINC-II had any other effects on the system, such as patient flow and patient engagement.

Surveys will be followed by an open-ended qualitative exploration to obtain details regarding perceptions of and experiences with care coordination, including concrete examples of connections between narcology and HIV care service delivery. It will explore organizational and systemic challenges that impede care coordination and opportunities to improve care coordination. Among LINC-II intervention participants, the role of LINC-II in addressing these issues and connecting people to both narcology and HIV care will be explored. We will conduct in-depth interviews with all providers and administrators and recruit a purposively chosen sub-sample of 30 participants from the LINC-II study. Interviews will be audio recorded, translated, and transcribed for analysis.

For administrators and providers in each system (n=26), all surveys and in-depth interviews will be conducted within 20-60 minutes and will occur at study launch, 12, and 24 months post-launch. This will not necessarily include the same providers and administrators at each assessment, in event of staff turnover. Written informed consent will be obtained prior to each interview. LINC-II study participants (N=240) will provide survey data on system perceptions at baseline, 6 and 12 month follow-up as part of their RCT study assessment. A subsample of participants selected for in-depth interview (n=30) will be interviewed subsequent to survey completion. Interviews will be audio recorded, translated, and transcribed for analysis. We will maintain a roster of interview refusals so as to consider potential biases in our sample of interviewees.

#### **5.4 ESTIMATES OF COST AND COST-EFFECTIVENESS**

Costs will be measured from the provider perspective and will include the cost of all resources utilized for each study participant from the date of randomization for a period of 12 months. Average provider cost per patient will then be stratified by study arm and outcome to generate cost-effectiveness estimates with 95% confidence intervals.

Resource or outcome	Method for estimating unit cost or cost/outcome
Resources	Method for estimating unit costs
Medications, laboratory tests, and other supplies	Types of antiretroviral and narcology medications and other drugs dispensed to study participants and types of laboratory investigations performed between study enrollment and the primary 12-month endpoint will be extracted from individual study records and clinic records for the intervention arm and from self-report and clinic records for the control arm. For each medication dispensed, a unit cost will be assigned that represents local investigators' best estimate of the procurement prices that study sites would have to pay if they adopted the intervention as standard care, using data from invoices and local medication price lists. For each type of laboratory test, the fee charged to conduct the test will be used as its unit cost. If a fee schedule is not available, a cost/test will be estimated using an ingredients costing method. Laboratory tests that are done solely for research purposes and are not likely to be included if the intervention were adopted as standard care will be excluded. Supplies that are used for individual patient care will be assigned a unit cost from procurement invoices.
Outpatient visits	An average unit cost per outpatient visit to each type of facility will be estimated by dividing total clinical staff cost per month by the number of visits made to the facility that month. If data are available to stratify this estimate by purpose of visit or staff cadre required, this will be done, but the overall average has proven to be sufficient for outpatient settings. Clinical staff salaries (total cost to the employer) for each staff cadre will be obtained from the study sites or the administrative entity responsible for the sites' payrolls.
Case manager costs	As case managers are an intervention-specific resource, costs will be calculated from study invoices and expenditure reports and estimated as an average cost per session conducted. Case manager transport, SMS fees, and other costs associated with this component of the intervention will be included in the cost/session estimate. (Although every patient in the intervention arm will be assigned a case manager, some patients will complete all ten planned sessions, while others will not. As participation in sessions may be associated with outcomes, a cost/session attended will be a more useful estimate than a cost per patient.)
Fixed costs--buildings and equipment and furnishings	The total floor space that is required for study-related service delivery, excluding research-specific activities such as administration of informed consent, will be measured in each facility, including a proportion of shared spaces such as waiting areas. If the study sites or local administrative entity use a standard cost/square meter for clinic space, this will be accepted as the cost of buildings. Otherwise, a market-related average rental cost per square meter will be applied to estimate the cost of the building. Utilities will be added as a percentage mark-up based on site-specific planning documents or other local sources. The replacement cost of equipment and furnishings will be obtained and an appropriate working life applied to each instrument to obtain an average cost/month. If laboratory instrument procurement costs are not included in lab fees, these will be estimated in the same way as other equipment costs. Total building and equipment and furnishing costs per month will be divided by the number of relevant clinic visits made each month to estimate a fixed cost/clinic visit.

Resource or outcome	Method for estimating unit cost or cost/outcome
Resources	Method for estimating unit costs
Fixed costs-- management and administration and general supplies	Costs of all staff members who do not provide direct patient care but provide some support to the delivery of study-related services (e.g. clinic manager, data clerks) will be calculated, with salaries obtained from the study sites or the administrative entity responsible for the sites' payrolls. The cost of general supplies (e.g. cleaning materials, stationery) will be obtained from facility financial reports. Total management, administration and supply costs per month will be divided by the total number of clinic visits made each month to estimate a fixed cost/clinic visit.
Outcomes	Methods for estimate cost/outcome
Cost/patient served	Total costs in study period/total number of patients enrolled, stratified by arm. This estimate is useful for budgeting purposes, as the difference between the arms indicates the additional budgetary resources needed to implement the intervention per patient served.
Cost/patient initiating ART	Total cost from enrollment to 28 days/total number of patients initiating ART within 28 days, stratified by arm. This estimate looks at the difference in cost between the intervention and standard care up to the point of ART initiation.
Cost/outcome	Total costs for patients stratified by arm and outcome. The difference in cost between outcomes indicates the anticipated difference in budgetary needs if outcomes improve.
Total cost/patient suppressed	Total cost from enrollment to 12 months/total number of patients achieving primary outcome of 12-month viral suppression, stratified by arm. This estimate focuses on cost differences between the arms for patients who do achieve the primary outcome. It takes into account all costs incurred for all patients but divides by only the number with a successful outcome, and thereby links the cost of service delivery to the primary outcome.
Cost-effectiveness	Incremental cost-effectiveness ratio (ICER) = Difference in costs (intervention arm-control arm)/ difference in outcomes (intervention arm-control arm). The ICER indicates the incremental additional cost to achieve one additional successful outcome.

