### 3.7.C. URINE

A pregnancy test will be administered by trained clinical research staff to all participants at screening and at each study visit for intervention participants. Pregnant women will be excluded from the study due to some reports suggesting possible adverse events with study medications. Participants found to be pregnant may have their implant removed but will still be followed-up for the duration of the study. For these participants the naltrexone implant will be removed (if removal is indicated) by clinical staff at Pavlov.

Urine will also be used to conduct urine drug testing on all intervention participants at all study visits and for control participants at the 6 and 12-month study visits. Urine drug tests must be negative for opioids before participants can receive the implant. Urine toxicology will test for a range of opioids, specifically opiates (products of the poppy plant – morphine, heroin, codeine) and synthetic opioids (specifically methadone). If new opioids appear on the scene in Russia, such as fentanyl, then we will begin testing for this, but currently that is not thought to be an issue.

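### The Cost/outcome row in section 5.4 gives a budget meaning to a cost gap between outcome groups, which is not a randomised comparison

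*Combined protocol and SAP*

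**What the plan says.** The outcomes part of the section 5.4 table has five rows. The Cost/outcome row is defined as "Total costs for patients stratified by arm and outcome" and is interpreted as follows: "The difference in cost between outcomes indicates the anticipated difference in budgetary needs if outcomes improve". No caveat, adjustment or assumption accompanies that sentence.

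Three other places bear on it:

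- Costing is cumulative over follow-up. It "will include the cost of all resources utilized for each study participant from the date of randomization for a period of 12 months" (section 5.4, opening), so a patient who attends and is dispensed more costs more.
- The case-manager row of the same table notes that "some patients will complete all ten planned sessions, while others will not", and adds: "As participation in sessions may be associated with outcomes, a cost/session attended will be a more useful estimate than a cost per patient".
- Section 3.7.C makes implant receipt conditional: "Urine drug tests must be negative for opioids before participants can receive the implant".

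The same table holds two between-arm measures. Cost/patient served takes the difference between arms as the extra budget needed per patient to run the intervention. The ICER is "Difference in costs (intervention arm-control arm)/ difference in outcomes (intervention arm-control arm"). The Aim 3 text under section 8.2 repeats the ICER but not the budget sentence.

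**The concern.** A patient's outcome group is known only at the end of follow-up. Comparing costs between those groups within an arm compares different kinds of patient, and randomisation does not balance them. Patients who keep appointments, pass the urine test before an implant and collect ART will tend both to use more resources and to be suppressed more often. The gap then mixes engagement and prognosis with whatever being suppressed really costs, such as continuing ART supply.

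The budget sentence treats the gap as a prediction of what changes when outcomes improve. Aim 3 is meant to inform policy makers about scale-up. A reader of the results would meet two figures described in budget terms, Cost/outcome and Cost/patient served, with no rule for choosing between them.

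**Working it through.** **No cost figure to reproduce.** The documents state no unit cost, session count or cost by outcome. The only design figures borrowed are the suppression rates in section 2.8.A: 27% in the intervention arm and 10% in the control arm, a difference of 0.17. As a check on these, 96 evaluable patients per arm with a continuity-corrected chi-square test (two-sided 0.05 taken, since sidedness is not stated) give power of 0.818 against the stated 80%. The row says only outcome; I take 12-month suppression. Every cost below is an assumption.

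**Quantities compared.** Let p1 and p0 be the suppression rates in the intervention and control arms, and Cs and Cu the mean costs of suppressed and unsuppressed intervention patients.

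- Gap = Cs − Cu.
- Randomised cost per additional suppressed patient = (mean cost, intervention − mean cost, control) / (p1 − p0).

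**Illustration 1: case-manager sessions as the cost unit, none used by controls.** Mean sessions per intervention patient = 0.27 × Cs + 0.73 × Cu.

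| Sessions, suppressed vs unsuppressed | Gap | Mean per patient | Per additional suppressed (mean / 0.17) | Ratio to gap |
|---|---|---|---|---|
| 10 vs 10 | 0 | 10.00 | 58.8 | undefined |
| 9 vs 6 | 3 | 6.81 | 40.1 | 13.4 |
| 9 vs 3 | 6 | 4.62 | 27.2 | 4.5 |
| 10 vs 2 | 8 | 4.16 | 24.5 | 3.1 |

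As the gap rises, the randomised figure falls. The gap is therefore not a scaled version of the quantity a planner needs.

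**No treatment effect.** Suppose 10% are suppressed in both arms, with 9 vs 3 sessions. The gap is still 6 sessions. The programme spends 0.10 × 9 + 0.90 × 3 = 3.6 sessions per patient and adds no suppression.

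**Algebra for a resource that controls do not use.** When p1 > p0, the randomised figure minus the gap equals [p0 × Cs + (1 − p0) × Cu] / (p1 − p0), which is never negative. Check with 9 vs 3: 3.6 / 0.17 = 21.2, and 27.2 − 6 = 21.2.

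**Illustration 2: all resources, with control costs allowed.** Assume half the intervention arm engages (cost 100, 49% suppressed) and half does not (cost 40, 5% suppressed).

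- Suppressed: 0.5 × 0.49 + 0.5 × 0.05 = 0.27.
- Cs = (0.5 × 0.49 × 100 + 0.5 × 0.05 × 40) / 0.27 = 94.4.
- Cu = (0.5 × 0.51 × 100 + 0.5 × 0.95 × 40) / 0.73 = 61.0.
- Gap = 33.5 (from unrounded means). Arm mean = 0.5 × 100 + 0.5 × 40 = 70.

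| Assumed control mean cost | Arm difference | Per additional suppressed (/ 0.17) | Ratio to gap |
|---|---|---|---|
| 14.5 | 55.5 | 326 | about 10 |
| 50 | 20 | 118 | 3.5 |
| 60 | 10 | 59 | 1.8 |
| 64.3 | 5.7 | 33.5 | 1.0 |

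Above a control cost of 64.3 the ratio falls below 1. Once controls use the resource too, the direction of the error is no longer fixed.

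**The case against.** The best defence is that the table already answers the questions that matter. Cost/patient served gives the budget to implement, the ICER gives the cost of one more success, and both compare arms. The Cost/outcome row does not claim to be the cost of producing suppression. Part of any gap is a real recurrent cost of suppressed patients, which a budget holder may want to know. The remark on session attendance was made to justify costing per session, and it says only that an association may exist.

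Most of this stands. It limits the weight of the point and shows that the stratified costs are worth reporting as description. It does not rescue the sentence, which goes beyond description to say what happens to budgets if outcomes improve.

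Three stronger readings are tempting, and the documents do not support them:

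- *That Aim 3 as a whole is compromised.* One row's interpretation is at fault. The ICER and Cost/patient served do not depend on it, and the Aim 3 text in section 8.2 does not repeat it.
- *That the row omits spending on patients who engage but are not suppressed.* It does not. Those costs sit in the unsuppressed group, where they raise Cu and narrow the gap.
- *That the gap is about ten times too small.* That ratio needs one particular assumed control cost, and it sets a per-patient gap beside an ICER. With the same inputs, moving one patient from not engaged to engaged costs 60 and adds 0.49 − 0.05 = 0.44 suppression, or 60 / 0.44 = 136 per success, about four times the gap.

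**Conclusion.** The point holds as one of interpretation. The Cost/outcome gap compares groups defined after randomisation, and the budget meaning attached to it does not follow. Under the assumptions shown, the randomised cost per additional suppressed patient runs from about 1 to 10 or more times the gap. With no treatment effect the gap can still be positive. Because the documents give no costs, the actual size and direction are unknown. That engagement drives both cost and outcome is a well-founded expectation from sections 5.4 and 3.7.C, not something the documents demonstrate. No test, primary result or ICER changes. What changes is which figure may support a statement about budgets.

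**What to change.** In the Cost/outcome row of section 5.4:

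1. Delete the sentence that gives the difference between outcomes a budget meaning.
2. Label cost by arm and outcome as descriptive only.
3. State that budget and scale-up conclusions rest on the between-arm difference in cost per patient served and on the ICER.

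Both of those measures are already planned. The cost is a few lines of wording. No new data or analysis is needed, and the Aim 3 text in section 8.2 can stay as it is.

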**Figure: LINC-II Study Design**

Throughout the course of the study, participants will be expected to participate in three in-person assessments and blood draw visits (baseline, 24 weeks and 52 weeks). Intervention participants will receive 4 naltrexone implants while in the study. Ideally, implants will be inserted every 10-12 weeks starting at week 4 post-study enrollment (weeks 4, 16, 28, 40). Participants will be invited to come in every 4 weeks following implantation for medication visits. Ideally, medication visits will occur at weeks 4, 8, 12, 16, 20, 24, 28, 32, 36, 40, 44, 48, and 52. Full study assessments occur at weeks 24 and 52 (in addition to medication visit procedures). Implant visits 2, 3, and 4 will involve the collection of blood for laboratory testing to monitor liver toxicity.

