#### 2.8.A. SAMPLE SIZE CALCULATION AND POWER

We provide power calculations for the key hypotheses to be tested in this RCT. Sample size calculations assume an alpha level of 0.05 and 240 patients enrolled into the trial.

**Aim 1: primary study outcome, undetectable viral load at 12-months post randomization:** Based on data from the LINC study, we expect 10% of controls will have undetectable viral load at 12 months. Given this and assuming 20% loss to follow-up (i.e., 192 evaluable subjects) the study will have 80% power to detect an absolute difference of 17% (i.e., 27% vs. 10% in the intervention and control arms, respectively) using a chi-square test with continuity correction. We anticipate larger effects may be observed in our study, which would result in even higher power.

**Aim 1: secondary study outcome, retention in HIV care (within 12 months):** Because this secondary outcome will be assessed using medical records, we expect loss to follow-up to be minimal and estimate 10% loss to follow-up due to death and subject withdrawals. Based on data collected from LINC, we expect 20% of controls will attend 2 appointments in 12 months. Based on these assumptions and with 216 evaluable subjects, the proposed study has 80% power to detect an absolute difference of 19% (i.e., 39% vs. 20% in the intervention and control groups, respectively) in the proportions retained in HIV care, based on a chi-square test with continuity correction.

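### Section 5.4 reads two cost-per-success ratios as cost differences between arms, and specifies no true cost difference at 28 days

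*Combined protocol and SAP*

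**What the plan says.** The outcomes part of the table in section 5.4 has five rows. Two of them divide an arm's total cost by its number of successes:

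- *Total cost/patient suppressed*: all costs from enrolment to 12 months, over the number suppressed at 12 months, by arm. The stated reading is "This estimate focuses on cost differences between the arms for patients who do achieve the primary outcome". The sentence after that says that every patient's cost is counted but only successes are in the denominator.
- *Cost/patient initiating ART*: all costs from enrolment to day 28, over the number who start ART by then, by arm. The stated reading is "This estimate looks at the difference in cost between the intervention and standard care up to the point of ART initiation".

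The other three rows are *Cost/patient served* (total cost over patients enrolled, with the between-arm difference read as the extra budget per patient), *Cost/outcome* (cost by arm and outcome) and *Cost-effectiveness* (the ICER).

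The Aim 3 text in section 8.2 describes the all-costs-over-successes ratio without calling it a difference. It bases cost-effectiveness on incremental cost per incremental outcome, and it plans 95% confidence intervals for average costs.

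**The concern.** In both rows the formula and the stated reading describe different quantities. The suppression ratio is not the cost of patients who succeed, because its numerator holds everyone's cost. In neither row is the gap between arms a cost difference, because it also depends on how many succeeded in each arm. A more effective intervention that costs more per patient can therefore appear under a cost-difference label with a negative sign.

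The ART row has a further mismatch. It claims to run to ART start, but it counts a fixed 28 days for everyone. That includes costs after ART start (section 3.3.B describes a first supply of one month) and the costs of people who never start.

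Aim 3 in section 2.1 is meant to inform policy makers about scaling up. For affordability, the first question is whether the intervention costs more and by how much. Two figures in one table, both described as between-arm cost differences and possibly opposite in sign, would blur that answer.

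**Working it through.** **Inputs.** Section 2.8.A gives the planning rates, "27% vs. 10% in the intervention and control arms, respectively", for viral suppression. It assumes 20% loss to follow-up, leaving 192 evaluable (96 per arm). The documents give no cost figures and no 28-day initiation rates. Below, *C* is the control cost per patient and *kC* the intervention cost per patient, and the values of *k* are assumptions.

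**The plan's own figure.** The rates come from the power statement, so that was checked first, with two-sided alpha 0.05 (the plan does not state sidedness). The pooled-variance formula is

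m = [1.96·√(2 × 0.185 × 0.815) + 0.842·√(0.10 × 0.90 + 0.27 × 0.73)]² / 0.17² = 80.7.

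With the continuity correction, n = (m/4)·[1 + √(1 + 4/(m × 0.17))]² = 92.1, so 93 per arm. At 96 per arm, power is 81.8% by this formula and 83.2% by exact enumeration of the corrected test. The stated 80% is reproduced to within 2 points by the formula.

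**What the ratio is.** For an arm with N patients, mean cost c and success rate p, total cost over successes = Nc/(Np) = c/p. Control gives C/0.10 = 10C. Intervention gives kC/0.27 = 3.70kC. They are equal at k = 0.27/0.10 = 2.7.

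**Gap between ratios, set against the true quantities at 12 months:**

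| k | Gap between the two ratios | Mean cost difference per patient, (k − 1)C | ICER, (k − 1)C/0.17 |
|---|---|---|---|
| 1.5 | 5.56C − 10C = −4.44C | +0.5C | 2.94C |
| 2.0 | 7.41C − 10C = −2.59C | +1.0C | 5.88C |
| 2.5 | 9.26C − 10C = −0.74C | +1.5C | 8.82C |
| 2.7 | 0 | +1.7C | 10C |
| 3.0 | 11.11C − 10C = +1.11C | +2.0C | 11.76C |

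For k strictly between 1 and 2.7 the gap has the opposite sign to the cost difference. What the sign does show is whether the ICER lies below the control arm's average cost per success: when the intervention arm has the higher success rate, kC/p_I < C/p_C is algebraically the same as (k − 1)C/(p_I − p_C) < C/p_C.

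**Loss to follow-up.** Suppose untested patients keep their costs but cannot count as successes, and 80% are tested in each arm. The ratios become C/(0.8 × 0.10) = 12.5C and kC/(0.8 × 0.27) = 4.63kC. The threshold stays at 2.7. At k = 2 the gap is 9.26C − 12.5C = −3.24C and the ICER is C/(0.8 × 0.17) = 7.35C. If the tested share differs by arm (assumed range 70% to 90%), the threshold runs from 2.7 × 0.7/0.9 = 2.10 to 2.7 × 0.9/0.7 = 3.47.

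**ART row.** The algebra is the same, and the threshold is the intervention initiation rate over the control rate. With assumed rates only: 20% vs 10% gives 2.0, 50% vs 20% gives 2.5, 70% vs 10% gives 7.0 and 50% vs 5% gives 10.

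**What else the table supplies.** At 12 months, *Cost/patient served* gives the mean cost difference, *Cost/outcome* gives the cost of those who succeed, and the last row gives the ICER. At 28 days there is no counterpart: *Cost/patient served* covers the whole study period, and no row names an ICER for ART initiation.

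**Boundary at day 28.** The study design text says: "Ideally, implants will be inserted every 10-12 weeks starting at week 4 post-study enrollment (weeks 4, 16, 28, 40". Week 4 is day 28, so ordinary scheduling can move the first implant's cost into or out of the 28-day figure, in the intervention arm only.

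**The case against.** The strongest reply is that the table should be read as a whole. *Cost/patient served* would show any higher cost of the intervention, and the ICER would be positive beside it. The suppression row itself says that all costs are in the numerator. Section 8.2 describes the ratio correctly, and a lower cost per success next to a higher cost per patient is not a contradiction, since they are different quantities. Aim 3 also sits under exploratory analyses in section 8.2.

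Most of this stands for 12 months. A reader might infer that Aim 3 would report a saving, or that its cost-effectiveness method is wrong. The documents do not support either: the ICER and the cost per patient served are correctly specified, and section 8.2 has no faulty sentence to repair. A reader might also carry the 2.7 over to the ART row, but there are no initiation rates from which to derive a threshold.

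The reply does not excuse the two sentences, which attach a cost-difference reading to formulas that do not produce one. Nor does it cover 28 days, where the table has no correct row to set beside the misread one.

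On the implant, one might want naltrexone taken out of the 28-day cost because it plays no part in starting ART. That would conflict with the plan's rule in section 5.4 of costing all resources used, it would drop part of the tested package, and it would make the intervention look cheaper. Week 4 is also only the ideal timing.

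**Conclusion.** Both readings are wrong as written. For the suppression row, at 27% vs 10% and equal loss to follow-up, the gap between arms has the wrong sign as a cost difference whenever the intervention costs more than control but less than 2.7 times as much per patient. That threshold moves with the observed rates, and it spans 2.10 to 3.47 if the tested share differs between arms within 70% to 90%. For the ART row only the form of the threshold is known.

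The consequence differs by horizon. At 12 months the defect is one interpretive sentence, because the correct quantities are already planned and only a confidence interval on the cost difference is not explicit. At 28 days it goes further: the plan promises a difference in cost and specifies nothing that delivers one. The trial's primary clinical conclusion is not affected.

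**What to change.** In section 5.4:

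1. Describe both ratios as average cost per success within each arm, and delete the two sentences that read them as cost differences.
2. For 12 months, take the cost difference from *Cost/patient served*, with a 95% confidence interval on the difference, and cost-effectiveness from the ICER.
3. For 28 days, add the mean cost per randomised participant by arm, the between-arm difference with a 95% confidence interval, and the incremental cost per additional ART initiator.
4. State that the 28-day figure covers a fixed 28 days for every participant and does not stop at ART start.
5. Optionally, show the 28-day figure with and without the cost of the first implant visit as a sensitivity analysis. Keep naltrexone in the main figure.

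The cost is a few edited sentences and a few extra lines of analysis on data already planned.
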